4.6 Testing Requirements

Testing requirements for the trial are listed in table 1.

TABLE 1: Minimum Screening and Follow-up Requirements

	Scr / BL	Proc / Disc	Act	1 Mo	4 Mo	10 Mo
Informed Consent	X					
Medical History	X					
Audiological and Hearing Aid History	X					
Current Medications	X		X	X	X	X
Adverse Events			X	X	X	X
Device Settings			X	X	X	X
Testing Requirements						
APHAB Questionnaire	X				X	X
Esteem® Questionnaire					X	X
Otoscope Exam (perform prior to testing)	I/N		I	I	I	I
Tympanogram	I/N		I	I	I	I
Air Conduction Thresholds	I/N		I	I	I/N	I/N
Air Conduction – Aided (Implant) Ear Warble Tone	I			I	I	I
Bone Conduction Thresholds	I/N		I	I	I/N	I/N
Most Comfortable Listening Level (MCL)	I/N		I	I	I	I
Uncomfortable Listening Level (UCL)	I/N		I	I	I	I
Speech Reception Threshold (SRT) – unaided	I/N					
Speech Reception Threshold (SRT) – aided	I/N		I	I	I	I
Word Recognition – unaided	I/N					
Word Recognition – aided	I/N		I	I	I	I
Envogram IT			X	X	X	X
CT Scan	X					
X-ray of implanted device (optional)		X				

I=Implanted Ear

N=Non-Implant Ear

4.6.1 Device Revisions / Interventions

There is also a possibility that post-implant, a surgical intervention may be required to repair, replace or completely remove some or all of the components of the *Esteem® System* due to device failure, malfunction or as a result of an adverse event. The surgical procedure may be performed in one of two ways: either through the subject's original incision or through the external ear canal; depending on the scope of the intervention. The surgical procedure may be performed under local or general anesthesia at the discretion of the surgeon.

A description of the recommended procedure that will be followed for each revision method is listed below:

4.6.1.1 Mastoid Approach (through the original incision)

- The original incision will be opened to expose the Sound Processor (SP).
- The Driver and Sensor lead will be disconnected from the SP.
- The capacitance of the Driver and Sensor will be tested.
- The Driver and Sensor will be tested. All or some of the intra-operative testing may be performed in order to evaluate the system.
- The test results will be evaluated to determine if the Driver and Sensor are functioning correctly. If one or both are not performing as expected the non-functioning part will be removed and replaced with a new part following the standard implant techniques outlined above. The new part will be tested to verify correct function.
- The Driver and Sensor will be connected to the Sound Processor, system testing will be performed and the wound closed.

4.6.1.2 Ear Canal Revision

This approach will only be used to give access to the Driver/stapes interface. No part of the device will be removed or replaced using this approach. It is possible that the bone cement may be removed and reapplied.

- An incision will be made in the ear canal close to the tympanic membrane (TM).
- The TM will be lifted away to expose the Driver/stapes interface for evaluation.
- If the bone cement requires replacement the old cement will be removed and new cement will be placed.
- Laser Doppler Vibrometer (LDV) measurements may be made.
- The TM will be replaced and the outer ear canal will be packed.

All revisions will be documented in the subject CRFs.

4.6.2 Removal of Subjects from Study

All subjects enrolled in this study are subject to complete clinical follow-up and will be included in the analysis of safety and effectiveness, as appropriate.

A subject may be removed from the study for any of the following reasons:

- Subject has fulfilled Protocol Requirements
- Subject did not receive the implant
- Subject withdraws consent
- Subject is lost to follow-up

- Subject has an inter-current illness that precludes follow-up
- Subject does not comply with the protocol
- Subject dies
- Investigator believes that it is in the best interest of the subject
- Sponsor terminates the study

If the subject completes or is withdrawn from the study the reason will be recorded on the CRF along with any relevant information concerning any device explant, subject death, and autopsy.

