- Noise, distortion, or poor fidelity
- Non-implant of the device due to fit or function of the device

- Dizziness when test vibrations are delivered to the stapes (middle ear bone)
- Feedback/whistling or squealing from the device
- Fibrotic growth/keloid formation (growths around the scar tissues or around the device)
- Infection of the Sound Processor pocket
- Injury to the middle ear bones because of physical contact with the Sensor/Driver portion of the device
- Partial or total loss of remaining hearing on implanted ear due to device failure
- Stimulation of the chorda tympani branch of the facial nerve
- Stimulation of the facial nerve
- Subluxation of the stapes as a result of cement removal during revision or explantation of the *Esteem® System*
- Transient or permanent injury to the hearing (auditory) nerve of the test ear with subsequent hearing loss due to the physical vibration of the stapes by the Driver portion of the device
- Accumulation of air under the scalp around the Sound Processor due to inadvertent nose blowing after the operation

Potential risks to the ear include infection of the ear. Risks specific to the middle ear include but are not limited to the following:

- Fullness or stuffy sensation in the ear
- Middle ear infection
- Ossicular necrosis or deterioration of the middle ear bones over time
- Hearing loss secondary to other risks of the middle ear
- Reconstruction of the bony ossicular chain due to resection of the long process (arm) of the incus bone

Potential risks of cochlear damage include but are not limited to the following:

- Damage to the cochlea (inner ear) due to excessive pressure from the *Esteem System*
- Damage to the cochlea (inner ear) associated with performing intra-operative testing
- Excessive electrical stimulation from the device of the inner ear
- Excessive vibration of the inner ear
- Hearing loss secondary to other risks to the inner ear
- Insufficient stimulation of the inner ear

Potential risks associated with anesthesia include but are not limited to the following:

- Neurological complications due to an increase in general anesthesia time above that normally associated with mastoid surgery
- Reaction to anesthesia
- Allergic reactions

Potential risks associated with a second surgical procedure (a transcanal middle ear surgery) include but are not limited to the following:

- Disruption of the Sensor when lifting the eardrum
- Drainage from the ear canal
- Infection

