4.3 Surgical Procedure

The surgical procedure for the implantation of the *Esteem® System* is outlined below. Subjects will be considered enrolled in the trial once they have signed the Informed Consent Form.

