4.3.1 Preparation of the subject and *Esteem® System* placement

- a) The subject will be anesthetized.
- b) Prepare subject for intra-operative testing
- c) Ensure that a facial nerve monitor is positioned to monitor the facial nerve during the procedure (use of this at surgeon discretion).
- d) The replica Sound Processor may be used for determination of initial incision placement.
- e) The incision will be made and the ear retracted for the creation of the mastoid cavity.
- f) Use the replica Sound Processor to create a bed in the largest flat area of the temporal bone. The bed should be positioned so that the Sound Processor will lie as flat as possible without rocking. Note: The Sound Processor bed should be drilled first to prevent excess bone dust from getting into the facial recess. In addition, when drilling the SP bed care should be taken to prevent any penetration of the dura. A thin layer of bone should remain in the bottom of the SP bed for the SP to rest on. If the SP bed is drilled after the facial recess has been opened the facial recess and mastoid cavity should be packed to prevent bone dust from accumulating in the middle ear.
- g) Create a channel for placement of the Driver/Sensor leads.
- h) The facial recess will be opened to allow placement of the Driver.
- i) Throughout the procedure the surgical site should be continuously irrigated with antibiotic solution.
- j) Upon completion of the mastoidectomy and prior to separation of the ossicular chain, perform baseline test for comparison to *Esteem® System* implanted components and record results.
- k) Separate the incus from the stapes and resect approximately 1mm to 3mm from the long process of the incus.

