4.3.3.1 Intra-operative Driver Testing

- a) Connect the Driver to the driver cable.
- b) Check the capacitance of the Driver and compare to pre-positioning value. If the value is not within +/- 10% of the labeled value remove the Driver and do not use. Record the post-implant capacitance on the CRF.
- c) Conduct Laser Doppler Vibrometry (LDV) test to measure stapes displacement.
- d) Compare the Driver signal strength at 1Vrms to the acceptance range according to the ISA.
- e) Record the capacitance, and intra-operative test results.

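### A study subject whose implant surgery is started and then abandoned has no assured place in the Objective 3 and 4 safety counts and no scheduled 1-month assessment

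*Combined protocol and SAP*

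**What the plan says.** Section 4.6.2 opens with a general rule: "All subjects enrolled in this study are subject to complete clinical follow-up", and they "will be included in the analysis of safety and effectiveness, as appropriate". It then lists reasons for which a subject may be removed, among them "Subject did not receive the implant". Enrolment is early. Under section 4.3, "Subjects will be considered enrolled in the trial once they have signed the Informed Consent Form".

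The plan foresees that an implantation may not be completed. Section 3.2 lists "Non-implant of the device due to fit or function of the device" among the risks.

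The surgical steps come in this order. In section 4.3.1, "The facial recess will be opened to allow placement of the Driver" (step h), and the surgeon is later told to "Separate the incus from the stapes and resect approximately 1mm to 3mm from the long process of the incus" (step k). Placement of the Driver and Sensor follows in 4.3.2, and testing in 4.3.3. For the Driver, section 4.3.3.1 says: "If the value is not within +/- 10% of the labeled value remove the Driver and do not use". Section 4.3.3.2 has the same rule for the Sensor.

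Section 4.7 makes up the 109 safety subjects from the 45 newly implanted subjects and a chart review of commercial cases. Section 4.5.3 places the 1-, 4- and 10-month visits after activation. Table 1 marks adverse events at Activation and later visits, but not at the procedure/discharge column. Objective 4 in section 5.2 is assessed at 1 month and succeeds if the one-sided 95% exact upper bound is below 7%.

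**The concern.** Objective 4 asks how often facial paresis or paralysis occurs when newly trained surgeons operate. The facial recess is opened before any device component is in place, so a subject whose operation stops after that point has had the surgical exposure whether or not a device is left in. The natural population for this objective is everyone in whom implant surgery was started. The plan describes those who were implanted, and adds a removal reason wide enough to take out the difference between the two groups.

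The visit schedule compounds this. Without a device there is no activation, and without activation the plan defines no 1-month visit. Even a site that kept such a subject would have no protocol date for the Objective 4 assessment. Objective 3 has a related gap: serious device effects are counted over person-months at each follow-up, and these subjects have no scheduled follow-up after activation.

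At stake are a primary safety rate that might be understated, and the scheduled safety follow-up of a small group who had surgery without receiving the device.

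**Working it through.** **Inputs.** Null rate 7%, assumed true rate 2%, 109 subjects and at least 80% power (section 5.1). One-sided 95% exact binomial upper bound, success if below 7% (section 5.2, Objective 4). Prospective subjects 45 (section 4.7), so chart-review cases number 109 − 45 = 64. The documents give no abandonment rate and no paresis rate among abandoned attempts.

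**1. Reproduce the plan's figure.** The exact upper bound U for x events in n solves P(X ≤ x | n, U) = 0.05, which is the 95th percentile of Beta(x + 1, n − x).

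- 3/109: U = 6.96%, success. 4/109: U = 8.20%, failure. The rule is therefore at most 3 events.
- Type I error: P(X ≤ 3 | 109, 0.07) = 0.0485.
- Power: P(X ≤ 3 | 109, 0.02) = 82.5%.
- At n = 108 only 2 events are allowed and power is 63.3%, so 109 is the smallest n with at least 80% exact power.

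The stated sample size reproduces.

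**2. Put abandoned attempts back into numerator and denominator.**

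| Implanted only | Added | All attempts | Upper bound | Result |
|---|---|---|---|---|
| 3/109 (6.96%) | 1 attempt, 1 paresis | 4/110 | 8.13% | fails |
| 3/109 | 3 attempts, 1 paresis | 4/112 | 7.99% | fails |
| 3/109 | 5 attempts, 1 paresis | 4/114 | 7.85% | fails |
| 3/109 | 1 attempt, none | 3/110 | 6.90% | passes |
| 3/109 | 5 attempts, none | 3/114 | 6.66% | passes |
| 2/109 (5.66%) | 1 attempt, 1 paresis | 3/110 | 6.90% | passes |

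One omitted case reverses the result only when exactly 3 events are otherwise seen. At the planned 2% rate that probability is P(X ≤ 3) − P(X ≤ 2) = 82.5% − 62.8% = 19.7%.

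**3. Size of the bias, by assumption.** Let the true rate over all attempts be 7%, f the fraction abandoned and q their paresis rate. The rate among implanted subjects is then (0.07 − f·q)/(1 − f), and the chance of false success is P(X ≤ 3) at that rate. The first result column drops abandoned attempts from all 109. The second drops them only from the 45 prospective subjects and leaves the 64 chart-review cases at 7%, adding the two binomial counts.

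| f | q | Implanted rate | False success, all 109 | False success, the 45 only |
|---|---|---|---|---|
| 1% or 5% | 7% | 7.00% | 4.8% | 4.8% |
| 1% | 20% | (0.07 − 0.002)/0.99 = 6.87% | 5.4% | 5.05% |
| 1% | 50% | (0.07 − 0.005)/0.99 = 6.57% | 6.7% | 5.6% |
| 5% | 20% | (0.07 − 0.010)/0.95 = 6.32% | 8.1% | 6.0% |
| 5% | 50% | (0.07 − 0.025)/0.95 = 4.74% | 23.6% | 9.7% |

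The values of f and q are illustrations, not estimates.

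**4. Cost in power of keeping these subjects.** At a true 2%, power is 82.1% at n = 110 and 80.5% at n = 114, still above the stated 80%.

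**The case against.** The strongest reply is that section 4.6.2 already answers the point: its first sentence brings every enrolled subject into follow-up and the safety analysis, and enrolment is at consent. The removal list is permissive, and leaving the study is not the same as having collected data discarded. Where the plan wants data excluded it says so: section 4.2 drops audiometric data for subjects who do not meet the hearing-aid fit check, and expressly keeps their safety data at least through 1 month. The removal reason also has an ordinary use, because surgical consent precedes the CT scan and further audiology, so some enrolled subjects will never reach the operating room.

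Much of this stands. Removal is allowed, not required. Events before discharge are recorded (section 4.4), post-surgical visits may be held as needed (4.5.1), and all adverse events go on a form (4.7.2). A reader might infer that injuries in abandoned cases would go unrecorded; the documents do not support that. What is missing is a scheduled 1-month assessment and an assured place in the counts. The inclusion sentence does not supply either, because its qualifier is undefined, section 4.7 describes the safety set by implantation, and no visit date exists without activation.

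Two further inferences go too far. Sections 4.3.3.1 and 4.3.3.2 tell the surgeon to discard an out-of-tolerance component; they do not say that the operation is then abandoned, and a replacement may follow. The evidence that abandonment is foreseen is the section 3.2 risk entry, which gives no frequency. Nor do the documents show that abandoned cases are harder or carry more paresis. That entry attributes non-implantation to device fit or function, and a faulty component need not mean a difficult dissection.

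**Conclusion.** The concern holds as a gap in the safety population and the visit schedule. A study subject operated on but not implanted can be removed under 4.6.2, has no scheduled 1-month assessment, and is not assured a place in Objectives 3 and 4.

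Downward bias in Objective 4 is conditional. It arises if paresis is more frequent in abandoned attempts than in completed ones. If it is equally frequent, false success stays at 4.8%. Under the illustrative assumptions above, it rises to between 5.05% and 9.7% if only the 45 prospective subjects are affected, which is the reach of section 4.6.2. It rises to between 5.4% and 23.6% only if the 64 chart-review cases omit abandoned attempts in the same way, on which the documents are silent.

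A reader might conclude that one omitted case would overturn the result in general. It does so only when exactly 3 events are otherwise counted, about a 20% chance at the planned 2% rate, and an abandoned subject also has paresis. That is a narrow condition, but it bears on a primary safety objective and can be removed cheaply.

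**What to change.** - In section 4.6.2, limit this removal reason to subjects in whom implant surgery was not started.
- In sections 4.7 and 5.2, define the safety set for Objectives 3 and 4 as all study subjects in whom implant surgery was started, with abandoned attempts in both numerator and denominator. They need not count toward the 45 efficacy subjects.
- Time safety data collection for these subjects from the surgery date, including an assessment for Objective 4 that does not depend on activation.
- Report the number of abandoned attempts.
- Apply the same rule to the chart-review cases where records allow, and state where they do not.

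The cost is a few sentences of protocol text and a few extra follow-up contacts. The safety rates may look slightly less favourable. Power at a true 2% rate stays at or above 80% with up to five added subjects, and the efficacy analyses are unaffected.

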4.7 Adverse Events

The 109 subjects to be reported for the Adverse Event endpoint will consist of the 45 newly-implanted subjects supplemented by data from a retrospective chart review of "commercial" (non-study subjects).

4.7.1 Definitions

Adverse Event (AE): An Adverse Event is any undesirable clinical event occurring to a subject, during a clinical trial, whether or not it is considered related to the investigational product. This includes a change in a subject's condition or laboratory results, which has or could have a deleterious effect on the subject's health or well-being, including failure of bone conduction/safety algorithm.

Serious Adverse Event (SAE): A Serious Adverse Event (SAE) or a Serious Adverse Device Effect (SADE) are events which:

- Results in death
- Is life threatening
- Results in persistent or significant disability / incapacity
- Results in a congenital anomaly / birth defect
- Requires or prolongs in-patient hospitalization (>24 hours)
- Requires intervention to prevent permanent impairment/damage

Unanticipated Adverse Device Effect (UADE): An Unanticipated Adverse Device Effect is any serious adverse effect on health or safety or any life-threatening problem or death caused by, or associated with, a device, if that effect, problem, or death was not previously identified in nature, severity, or degree of incidence in the investigational plan or application (including a supplementary plan or application), or any other unanticipated serious problem associated with a device that relates to the rights, safety, or welfare of subjects. NOTE: an UADE is, by definition, serious in nature.

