2. To demonstrate that the *Esteem® System* is as effective as or better than the hearing aid for improving speech discrimination (intelligibility) as shown by the word recognition score at 50 dB.

Endpoint: Comparison of the word recognition score using the *Esteem®* compared to the pre-implant aided condition.

3. To determine the incidence of Serious Adverse Device Effects (SADE) and Adverse Device Effects (ADE) and the incidence rate of device failures and replacements.

Endpoint: The analysis of the incidence of SADEs and device failures and replacements at each follow-up.

4. To demonstrate that the incidence of facial pareses/paralysis is no greater than the 7% incidence experienced in the PMA clinical trial.

Endpoint: The analysis of the incidence of facial pareses/paralysis at 1 month follow-up.

5. To demonstrate that the subjects' cochlear function remains unchanged with the *Esteem® System* as shown by comparison of the subjects' pre-implant baseline bone conduction threshold versus the subjects' post-activation visit bone conduction threshold.

Endpoint: Comparison of bone conduction threshold (BC) using forehead placement post activation compared to the pre-implant BC threshold.

Secondary Objectives:

1. To show that the *Esteem® System* improves Quality-of-Life when compared to the baseline aided condition as shown by APHAB results.
2. To gather subject feedback and comments on the use of the *Esteem® System* relative to the pre-implant hearing aid (aided condition) as shown by the *Esteem® Questionnaire*.

Sponsor Contact Information:

Envoy Medical Corporation, Inc. (EMC)

[name]

[name]

[contact]

Customer Service [contact]

www.envoymedical.com

Changes in Revision 04

Change footer revision number from Rev 03 to Rev 04
Clarify the enrollment totals for efficacy and safety endpoints in Protocol Summary, sections 1.4, 2.2 and 4.7
Change sponsor address of Envoy Medical Corporation to current address
Miscellaneous typo corrections

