2.2 Investigational Sites and Number of Enrollments

The post-approval study will enroll a minimum of 45 new subjects on a consecutive consenting basis at 5 to 10 investigational sites to be implanted by newly-trained surgeons. These subjects will be evaluated for both efficacy and safety endpoints. The goal will be to monitor the subjects through their one (1) year follow-up. NOTE: In order to achieve the required sample size of 109 subjects for the safety endpoints, data from these 45 new subjects will be supplemented by data from a retrospective chart review of "commercial" (non-study subjects).

Trial Objectives

The overall objective of the study is to evaluate the safety and effectiveness of the *Esteem® System* implanted by newly-trained surgeons in subjects suffering from moderate to severe hearing loss.

Primary Objectives:

- 1) To demonstrate that the *Esteem® System* improves the speech threshold of sensitivity for hearing and identifying speech signals as well as or better than the pre-implant hearing aid (aided condition).
Endpoint: Comparison of the speech reception threshold (SRT) using the *Esteem® System* as compared to the pre-implant aided condition.
- 2) To demonstrate that the *Esteem® System* is as effective as or better than the hearing aid for improving speech discrimination (intelligibility) as shown by the word recognition score at 50 dB.
Endpoint: Comparison of word recognition score using the *Esteem®* as compared to the pre-implant aided condition.
- 3) To determine the incidence of Serious Adverse Device Effects (SADE) and Adverse Device Effects (ADE) and the incidence rate of device failures and replacements.
Endpoint: The analysis of the incidence of SADEs and device failures and replacements at each follow-up.
- 4) To demonstrate that the incidence of facial pareses/paralysis is no greater than the 7% incidence experienced in the PMA clinical trial.
Endpoint: The analysis of the incidence of facial pareses/paralysis at 1 month follow-up.
- 5) To demonstrate that the subjects' cochlear function remains unchanged with the *Esteem® System* as shown by comparison of the subjects' pre-implant baseline bone conduction threshold versus the subjects' post-activation visit bone conduction threshold.
Endpoint: Comparison of the bone conduction threshold with forehead placement compared to the pre-implant bone conduction threshold.

Secondary Objectives:

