Additional Analyses: The Word Recognition Scores will be compared using the Thornton and Raffin (1978) published upper and lower limits for various word lists based upon percentage scores. Based upon this, an analysis of the % better than, % equal to and % below the aided condition (HA) will be presented.

Reference:

Objective 3: To determine the incidence rate of Serious Adverse Device Effects (SADE) and the incidence rate of device failures and replacements.

Endpoint: The analysis of the incidence of SADEs and device failures and replacements at each follow-up.

Hypotheses: There is no formal hypothesis. This objective is to provide an accurate estimate of the SADE rate and device failure and replacement rate associated with the *Esteem® System*.

Statistical Analyses: The incidence of SADEs and device failures and replacements will be estimated with the observed number of SADEs and device failures and replacements over the total person-months of follow-up at each follow-up. The upper bound of the one-sided 95% exact binomial confidence interval on the SADE rate and device failure and replacement rate will be calculated and reported.

Objective 4: To demonstrate that the incidence of facial pareses/paralysis is no greater than the 7% incidence experienced in the PMA clinical trial.

Endpoint: The analysis of the incidence of facial pareses/paralysis at 1 month follow-up.

Criterion for success: The 95% Upper Confidence Bound (UCB) for the incidence of facial paresis/paralysis ($p_{\text{paresis/paralysis}}$) is less than 7%

$$95\% \text{ UCB for } p_{\text{paresis/paralysis}} < 7\%$$

Statistical Analyses: The upper bound of the one-sided 95% exact binomial confidence interval on the incidence of facial paresis/paralysis will be compared to 7% and success declared if it is lower than 7%.

Objective 5: To demonstrate that the subject's cochlear function remains unchanged with the *Esteem®* system as shown by comparison of the subject's pre-implant baseline Bone Conduction Threshold (BCT) vs. the subject's post activation BCT.

Endpoint Analysis: Bone conduction will be measured with forehead probe placement. The Safety Algorithm as described in Attachment C, will be used for any Bone Conduction results outside the stability range.

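### SADE is defined by seriousness alone, with no device- or procedure-relatedness criterion, and the ADE incidence named in Primary Objective 3 has no definition, endpoint or planned estimate

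*Combined protocol and SAP*

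**What the plan says.** **Definitions (section 4.7.1).** An adverse event counts "whether or not it is considered related to the investigational product". The next entry covers two terms at once: "A Serious Adverse Event (SAE) or a Serious Adverse Device Effect (SADE) are events which" meet one of six criteria: death, threat to life, lasting or significant disability, congenital anomaly, hospital stay over 24 hours, or intervention to prevent permanent damage. UADE is the only category with a causal element, "caused by, or associated with, a device", and it is limited to unanticipated serious problems. ADE has no entry.

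**Reporting (section 4.7.2).** All adverse events go on an Adverse Event Form. The section describes no causality assessment, scale or assessor.

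**Objective 3.** The Protocol Summary states it as "To determine the incidence of Serious Adverse Device Effects (SADE) and Adverse Device Effects (ADE) and the incidence rate of device failures and replacements", and section 2.2 repeats this. The endpoint line under it in both places, and again in section 5.2, is "The analysis of the incidence of SADEs and device failures and replacements at each follow-up". Section 5.2 restates the objective as "To determine the incidence rate of Serious Adverse Device Effects (SADE) and the incidence rate of device failures and replacements". Its analysis paragraph says "The upper bound of the one-sided 95% exact binomial confidence interval on the SADE rate and device failure and replacement rate will be calculated". It sets no formal hypothesis and gives accurate estimation as the aim.

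**Safety set (sections 2.2 and 4.7).** The 109 subjects are 45 new subjects plus a retrospective chart review of commercial patients.

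**The concern.** Objective 3 is estimation only, so the event definition determines what the result means. If SADE and SAE share one definition, an unrelated hospital stay of more than 24 hours is a SADE, and the figure reported as a device-effect rate is a rate of serious illness from any cause.

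The make-up of the safety set adds to this. At the minimum enrolment of 45, 64 of the 109 subjects come from charts, and their events must be classified after the fact. Without a written rule, one source could be counted all-cause and the other device-related. The pooled rate would then have no clear meaning.

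The ADE gap is a separate matter. A primary objective names a quantity that the protocol does not define and for which it plans no overall estimate.

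**Working it through.** **1. Is there a plan figure to reproduce?** No. Objective 3 has no hypothesis, margin, power or sample size. The 109 comes from the facial paresis/paralysis objective in section 5.1 (null rate 7%, hypothesized true rate 2%, 1 month). The check is therefore a comparison of the texts plus one illustration.

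**2. Relatedness, term by term (section 4.7.1)**

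| Term | Seriousness required | Relation to device stated |
|---|---|---|
| AE | No | Counts regardless of relation |
| SAE | Yes, six criteria | None |
| SADE | Yes, the same six criteria | None |
| UADE | Yes | Yes, cause or association |
| ADE | Not defined | Not defined |

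The SAE and SADE rows are identical, so as written the two counts are identical.

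**3. Objective 3, place by place**

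| Place | SADE | ADE | Failures and replacements |
|---|---|---|---|
| Protocol Summary, objective | Yes | Yes | Yes |
| Protocol Summary, endpoint | Yes | No | Yes |
| Section 2.2, objective | Yes | Yes | Yes |
| Section 2.2, endpoint | Yes | No | Yes |
| Section 5.2, objective, endpoint and analysis | Yes | No | Yes |

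ADE falls out first between the objective and its own endpoint line, in the Protocol Summary and in section 2.2. Section 5.2 follows the endpoint line. Device failures and replacements are carried through consistently.

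**4. Illustration of size.** The documents give no SADE rate, so these counts are assumptions: 2 device-related serious events, and unrelated serious events in 2% to 5% of 109 subjects over a year (0.02 × 109 = 2.2 and 0.05 × 109 = 5.5, taken as 2 and 5). The exact one-sided 95% upper bound U for x events in n subjects solves P(X ≤ x | n, U) = 0.05, which is the 0.95 quantile of Beta(x + 1, n − x). With n = 109:

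- x = 2, device-related only: 2/109 = 1.8%, U = 5.66%
- x = 2 + 2 = 4: 4/109 = 3.7%, U = 8.20%
- x = 2 + 5 = 7: 7/109 = 6.4%, U = 11.72%

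**5. Sensitivity to follow-up.** One-year follow-up is stated only for the 45 new subjects; no length is stated for chart subjects. If each of 64 charts contributed one month (an assumption), exposure would be 45 + 64/12 = 50.3 subject-years. The unrelated events would then number 0.02 × 50.3 = 1.0 to 0.05 × 50.3 = 2.5. Totals of 3 to 5 events (2.5 rounded up to 3) give U = 6.96% to 9.40%. The direction is the same and the shift is smaller.

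**The case against.** The best defence is linguistic. The shared list can be read as defining only the word serious, with the words device effect supplying the relation to the device. On any other reading SADE is a redundant term. The Adverse Event Form, which is not in the documents, may also record relatedness; SADEs and ADEs could then be tabulated. Both arguments have force, so a reader should not infer that unrelated events will in fact be counted as SADEs, or that sites will each follow their own habit. The documents do not say how causality is or is not assessed. What survives is that the only written definition has no relatedness criterion, threshold or assessor. A field on a form would not set the counting rule, nor would it by itself cover events taken from charts.

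On ADE, a reader might infer that section 5.2 dropped it, or that the plan yields no information on device-related events. Neither is right. The omission begins in the endpoint lines of the Protocol Summary and section 2.2. Facial paresis/paralysis has its own estimate and bound under Objective 4. Failure of the bone-conduction algorithm is expressly an adverse event and is evaluated under Objective 5. What is missing is an overall ADE rate.

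It is also fair to say that over-counting unrelated events would overstate device harm and not hide it, and that no comparison of prospective with chart subjects is planned. Inconsistent counting would therefore matter through pooling.

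**Conclusion.** Both gaps stand. As written, the SADE definition makes the SADE rate an all-cause serious event rate, and ADE incidence is an undefined and unestimated part of a primary objective. Failures and replacements are unaffected.

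The consequence is limited to the reported safety estimate. A reader might infer that a success criterion is at risk, but Objective 3 has none.

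The move from 5.7% to between 8.2% and 11.7% is an illustration and not a forecast. It rests on assumed event counts, on a year of follow-up for all 109 subjects, and on subjects as the denominator, whereas section 5.2 divides events by person-months. It shows that a few unrelated events can raise the bound by about half or double it. This is a correction that should be made, in proportion to a wording fault in a primary safety endpoint.

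**What to change.** 1. In section 4.7.1, define ADE as an adverse event judged related to the device or implant procedure, and SADE as an ADE that meets the existing seriousness list. State the relatedness threshold and who makes the judgement.
2. State that the same definitions, threshold and assessor apply to the chart-review subjects.
3. Add ADE incidence to the Objective 3 endpoint lines in the Protocol Summary, section 2.2 and section 5.2, and to the restated objective and analysis in section 5.2. Give it an upper confidence bound from a method that matches the chosen denominator: exact binomial if the rate is a proportion of subjects, a person-time method if it is per person-month. Alternatively, remove ADE from the objective in the Protocol Summary and section 2.2.
4. Report all SAEs beside SADEs, so that the effect of the relatedness judgement is visible.

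The cost is wording, a relatedness field on the Adverse Event Form if it has none, and one more table.
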